6.2.1.2 Dosage Adjustments, Delays, Rules for Withholding or Restarting, Permanent Discontinuation

There will be no dose adjustments in this study. If, in the opinion of the investigator, a subject is unable to tolerate a specific dose of IP, that subject will discontinue IP but will continue to return for all other study procedures and measurements until the end of the study.

Subjects who are late for a Scheduled Dose of Investigational Product

Administration of IP should occur within the visit window for each scheduled visit. IP must never be administered within less than 7 days of a previous dose. If a subject arrives for a visit and IP was administered within less than 7 days prior the dose should not be administered, but all other study procedures should be conducted. These subjects will receive their next SC IP administration as previously scheduled.

Subjects who miss a Scheduled Dose of Investigational Product Completely

Subjects randomized to SC IP administration (evolocumab or placebo) who completely miss a scheduled visit or IP administration will continue in the study and receive scheduled study drug at the next scheduled visit.

6.2.2 Non-Amgen Investigational Product(s)

Non-Amgen investigational product(s) including ezetimibe 10mg PO and placebo PO will be used in this study.

6.2.2.1 Non-Amgen Investigational Product Ezetimibe

6.2.2.1.1 Dosage, Administration, and Schedule

Ezetimibe 10 mg tablets will be administered orally, once daily, with or without food, at a time convenient to the subject. To enable blinding of the PO IP, ezetimibe will be supplied as over-encapsulated 10 mg tablets.

Ezetimibe 10mg is an approved drug for the treatment of patients with hypercholesterolemia, familial hypercholesterolemia, and homozygous sitosterolemia (ZETIA® [ezetimibe]).

Subjects who miss a dose of ezetimibe will be advised to take the missed dose as soon as they can however subjects should not take more than one dose of ezetimibe per day; subsequent doses will be taken at the usual time. However, if the next scheduled dose would be due in less than 12 hours, the subject will be advised to omit the missed dose entirely and to take the next dose at the normal time. Consult the IPIM for additional information on ezetimibe.

6.2.2.1.2 Dosage Adjustments, Delays, Rules for Withholding or Restarting, Permanent Discontinuation

No dosage adjustment is necessary in patients with mild hepatic or renal impairment. No dosage adjustment is necessary in geriatric patients. Additional details regarding ezetimibe are provided in the IPIM.

6.3 Hepatotoxicity Stopping and Rechallenge Rules

Subjects with abnormal hepatic laboratory values (ie, alkaline phosphatase [ALP], aspartate aminotransferase [AST], alanine aminotransaminase [ALT], total bilirubin [TBL]) and/or international normalized ratio [INR] and/or signs/symptoms of hepatitis (as described below) may meet the criteria for withholding or permanent discontinuation of Amgen investigational product or other protocol-required therapies as specified in the Guidance for Industry Drug-Induced Liver Injury: Premarketing Clinical Evaluation, July 2009.

6.3.1 Criteria for Permanent Discontinuation of Amgen Investigational Product and Other Protocol-required Therapies Due to Potential Hepatotoxicity

Amgen investigational product and other protocol required therapies should be discontinued permanently and the subject should be followed according to the recommendations in [Appendix A](#) (Additional Safety Assessment Information) for possible drug-induced liver injury (DILI), if ALL of the criteria below are met:

- TBL > 2x upper limit of normal (ULN) or INR > 1.5
- AND increased AST or ALT from the relevant baseline value as specified below:

Baseline AST or ALT value	AST or ALT elevation
< ULN	> 3x ULN

- AND no other cause for the combination of the above laboratory abnormalities is immediately apparent; important alternative causes for elevated AST/ALT and/or TBL values include, but are not limited to:
 - Hepatobiliary tract disease
 - Viral hepatitis (eg, Hepatitis A/B/C/D/E, Epstein-Barr Virus, cytomegalovirus, Herpes Simplex Virus, Varicella, toxoplasmosis, and Parvovirus)
 - Right sided heart failure, hypotension or any cause of hypoxia to the liver causing ischemia.
 - Exposure to hepatotoxic agents/drugs or hepatotoxins, including herbal and dietary supplements, plants and mushrooms
 - Heritable disorders causing impaired glucuronidation (eg, Gilbert's Syndrome, Crigler-Najjar syndrome) and drugs that inhibit bilirubin glucuronidation (eg, indinavir, atazanavir)
 - Alpha-one antitrypsin deficiency
 - Alcoholic hepatitis
 - Autoimmune hepatitis
 - Wilson's disease and hemochromatosis
 - Nonalcoholic Fatty Liver Disease including Steatohepatitis (NASH)
 - Non-hepatic causes (eg, rhabdomyolysis, hemolysis)

6.3.2 Criteria for Conditional Withholding of Amgen Investigational Product and Other Protocol-required Therapies Due to Potential Hepatotoxicity

For subjects who do not meet the criteria for permanent discontinuation of Amgen investigational product outlined above and have no underlying liver disease, and eligibility criteria requiring normal transaminases and TBL at baseline or subjects with underlying liver disease and baseline abnormal transaminases, the following rules are recommended for withholding of Amgen investigational product and other protocol-required therapies:

- Elevation of either AST or ALT according to the following schedule:

Baseline AST or ALT value	AST or ALT elevation
Any	> 8x ULN at any time
Any	> 5x ULN but < 8x ULN for ≥ 2 weeks
Any	> 5x ULN but < 8x ULN and unable to adhere to enhanced monitoring schedule
Any	> 3x ULN with clinical signs or symptoms that are consistent with hepatitis (such as right upper quadrant pain/tenderness, fever, nausea, vomiting, jaundice).

- OR: TBL > 3x ULN at any time
- OR: ALP > 8x ULN at any time>>

Evolocumab should be withheld pending investigation into alternative causes of DILI. If investigational product(s) is withheld, the subject is to be followed according to recommendations in [Appendix A](#) for possible DILI. Rechallenge may be considered if an alternative cause for impaired liver tests (ALT, AST, ALP) and/or elevated TBL, is discovered and the laboratory abnormalities resolve to normal or baseline ([Section 6.3.3](#)).

6.3.3 Criteria for Rechallenge of Amgen Investigational Product and Other Protocol-required Therapies After Potential Hepatotoxicity

The decision to rechallenge the subject should be discussed and agreed upon unanimously by the subject, investigator, and Amgen.

If signs or symptoms recur with rechallenge, then evolocumab should be permanently discontinued. Subjects who clearly meet the criteria for permanent discontinuation (as described in [Section 6.3.1](#)) should never be rechallenged.

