3. EXPERIMENTAL PLAN

3.1 Study Design

This is a phase 3, multicenter, double-blind, randomized, ezetimibe controlled, parallel group study for evolocumab in hypercholesterolemic Japanese subjects unable to tolerate an effective dose of a statin. Subjects who meet all inclusion/exclusion criteria will be randomized with an allocation ratio of 2:2:1:1 into 4 groups: QM 420 mg SC evolocumab + QD PO placebo, Q2W 140 mg SC evolocumab + QD PO placebo, QM SC placebo + QD 10 mg PO ezetimibe, Q2W SC placebo + QD 10 mg PO ezetimibe. Randomization will be stratified by screening LDL-C level and baseline statin use. Randomization should occur within 5 – 10 days of the screening LDL-C evaluation used to determine eligibility. **Subjects on low or atypical statin therapy must be on a stable dose for at least 4 weeks prior to the screening and throughout the blinded portion of the study; the dose cannot be adjusted during screening and for the duration of the study.**

For blinding purposes, every subject will receive investigational product (IP) SC and PO. Patients will be provided with evolocumab or placebo through the use of an autoinjector (AI) or Personal Injector. Depending on availability either a single Personal Injector or 3 autoinjectors will be provided for monthly dosing. A single AI will be used for Q2W dosing. Evolocumab and corresponding placebo will be administered at the study site or at appropriate non-clinic setting per [Table 1](#) (Schedule of Assessments). PO placebo will be available to match PO ezetimibe through over-encapsulation. The SC IP dose frequencies of Q2W and QM will not be blinded.

Following the Week 12 visit, all subjects will self-administer IP in the non-clinic setting; subjects will return to the clinical site at W24, W36, W48 and W52 for subsequent visits.

There will be an end of study phone call at W54 (**Q2W subjects only**) for any potential adverse events, serious adverse events, or adverse device effects.

Central laboratory results of the lipid panel, ApoA1, ApoB, lipoprotein(a), and high sensitivity C-reactive protein (hsCRP) will be blinded during double-blind treatment. Investigators will be provided lipid results starting at week 24 until the end of study for each subject. All lipid results from posttreatment to week 24 will remain blinded until the unblinding of the clinical database.

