The study includes collection of biomarker samples, where approved by the institutional review board (IEC/IRB). Administration of PO IP (ezetimibe or placebo) will end with the week 12 visit for all subjects. Following the week 12 visit, subjects should be treated to standard of care in addition to receiving open label evolocumab.

Subjects will be encouraged to complete all planned visits regardless of their adherence to investigational product (IP) administration. Formal review of the accumulating blinded data by an independent Data Monitoring Committee (DMC) **will occur**.

The study endpoints are defined in [Section 10.1.1](#).

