6. TREATMENT PROCEDURES

Evolocumab (AMG 145), placebo SC, ezetimibe PO, and placebo PO are IPs in this study. An Investigational Product Instruction Manual (IPIM) containing detailed information regarding the storage, preparation, **destruction**, and administration of IP will be provided separately.

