- Obtain serum acetaminophen (paracetamol) levels
- Obtain a more detailed history of:
 - Prior and/or concurrent diseases or illness
 - Exposure to environmental and/or industrial chemical agents
 - Symptoms (if applicable) including right upper quadrant pain, hypersensitivity-type reactions, fatigue, nausea, vomiting and fever
 - Prior and/or concurrent use of alcohol, recreational drugs and special diets
 - Concomitant use of medications (including non-prescription medicines and herbal and dietary supplements), plants, and mushrooms
- Obtain viral serologies
- Obtain CPK, haptoglobin, LDH, and peripheral blood smear
- Perform appropriate liver imaging if clinically indicated
- Obtain appropriate blood sampling for pharmacokinetic analysis if this has not already been collected
- Obtain hepatology consult (liver biopsy may be considered in consultation with an hepatologist)
- Follow the subject and the laboratory tests (ALT, AST, TBL, INR) until all laboratory abnormalities return to baseline or normal. The “close observation period” is to continue for a minimum of 4 weeks after discontinuation of all investigational product(s) and protocol-required therapies.

The potential DILI event and additional information such as medical history, concomitant medications and laboratory results must be captured in corresponding eCRFs.

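### The recurrence rule in protocol 6.3.3 permanently stops evolocumab only, so during the blinded 12 weeks it does not itself require a permanent stop of oral IP

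*Protocol*

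**What the plan says.** Protocol section 6.3 has three parts.

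- **6.3.1 (permanent stop).** If all its criteria are met, "Amgen investigational product and other protocol required therapies should be discontinued permanently". The criteria are bilirubin or INR elevation, AST or ALT elevation, and no other cause immediately apparent.
- **6.3.2 (conditional hold).** For lesser abnormalities, "the following rules are recommended for withholding of Amgen investigational product and other protocol-required therapies". Its closing paragraph then speaks of withholding evolocumab alone. That paragraph allows rechallenge to be considered if an alternative cause is found and the laboratory values resolve.
- **6.3.3 (rechallenge).** The heading is "Criteria for Rechallenge of Amgen Investigational Product and Other Protocol-required Therapies After Potential Hepatotoxicity". The decision must be unanimous among subject, investigator and sponsor. On recurrence the text says "If signs or symptoms recur with rechallenge, then evolocumab should be permanently discontinued". Subjects who clearly meet 6.3.1 are never to be rechallenged.

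The trial is double-dummy. Section 3.1 says "For blinding purposes, every subject will receive investigational product (IP) SC and PO", and section 6 says "Evolocumab (AMG 145), placebo SC, ezetimibe PO, and placebo PO are IPs in this study". The oral component is temporary: "Administration of PO IP (ezetimibe or placebo) will end with the week 12 visit for all subjects" (section 3.1).

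**The concern.** A positive rechallenge is strong evidence that something the subject is taking is responsible. In a blinded double-dummy trial the site does not know which of the two products is active, so the stopping instruction should work without knowledge of the assignment. The 6.3.3 sentence does not. In a control subject the only active study drug is ezetimibe, and the sentence does not name it. Elsewhere, for example in 9.2.1, the protocol uses blinded terms for the subcutaneous and oral products, so the 6.3.3 wording looks like an oversight.

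What is at stake is the safety of a rare individual subject, through a specific instruction that misses the drug of interest if followed to the letter. No efficacy result, power figure or planned safety table depends on it.

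**Working it through.** The main check sets the provisions side by side. The plan states no figure to reproduce.

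**1. Scope of each provision.** Section 6.1 classes ezetimibe as a non-Amgen IP. I therefore read it as falling under other protocol-required therapies wherever section 6.3 uses that phrase.

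| Protocol section | Action | Reaches oral IP? |
|---|---|---|
| 6.3.1 | Permanent stop, if all criteria are met | Yes |
| 6.3.2, lead-in | Recommended withholding | Yes |
| 6.3.2, closing sentence | Withholding pending investigation | Names evolocumab only |
| 6.3.3, heading | Rechallenge criteria | Yes |
| 6.3.3, recurrence sentence | Permanent stop | Names evolocumab only |
| 6.2.2.1.2 (ezetimibe) | No hepatic stopping or recurrence rule; refers to the IPIM | No rule in the protocol |

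**2. The recurrence sentence applied to each kind of subject.**

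- *Randomized to evolocumab, Day 1 to Week 12:* the active drug is stopped. The rule works.
- *Anyone after Week 12:* there is no oral IP and everyone receives evolocumab. The rule works.
- *Randomized to ezetimibe, Day 1 to Week 12 (20 planned, 10 per dosing frequency):* read strictly, there is no evolocumab to stop. Read as covering all SC IP, it stops the placebo. On neither reading does it reach ezetimibe.

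**3. What else applies when signs recur in that third group.**

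- If 6.3.1 is met at recurrence, oral IP is stopped permanently under 6.3.1. However, 6.3.1 needs no other cause to be immediately apparent, while 6.3.2 allows rechallenge only after an alternative cause was found. That earlier explanation may keep 6.3.1 from applying.
- If only a 6.3.2 threshold is met, withholding of oral IP is recommended again, but this is not a permanent stop.
- Below those thresholds there is judgment: 6.2.1.2 (IP not tolerated, in the investigator's opinion), 8.3.1 (removal for a safety concern) and 9.1.1 (removal because of an adverse event).

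What remains uncovered is a required, permanent stop of oral IP on recurrence when 6.3.1 is not met.

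**4. How much time the gap has to operate.** Protocol Table 1 schedules chemistry at screening, Day 1, Week 8, Week 12 and Week 52, so Week 8 is the only on-treatment sample before oral IP ends. SAP Appendix B puts Week 2 on Day 15, Week 8 on Day 57 and Week 12 on Day 85. Protocol Appendix A says close observation "is to continue for a minimum of 4 weeks after discontinuation of all investigational product(s) and protocol-required therapies".

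Oral days left at the earliest rechallenge = Week 12 day − (hold day + wait in days).

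- Hold on Day 57, 28-day wait: 85 − (57 + 28) = 0.
- Most favorable use of the ±3-day visit windows, with the hold on Day 54 and Week 12 on Day 88: 88 − (54 + 28) = 6.
- Hold on Day 57, 14-day wait: 85 − (57 + 14) = 14.
- Unscheduled detection on Day 15, 28-day wait: 85 − (15 + 28) = 42.

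Appendix A does not say that rechallenge must wait for the observation period to end, so the 14-day case is shown as an assumption. With the four-week wait, the gap mostly needs an abnormality found by an unscheduled test before Week 8.

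**The case against.** The strongest reply is that the protocol does not leave a relapsing control subject unprotected, and most of that reply stands. Section 6.3.1 still applies at a recurrence. Section 6.2.1.2 sits in the evolocumab part, but it is worded for IP, which includes ezetimibe, and it describes a stop rather than a hold. Sections 8.3.1 and 9.1.1 allow removal without any laboratory threshold, and 5.2 allows unblinding when it is essential to management. Every rechallenge is an individual decision that the sponsor has agreed to, so a site is unlikely to act on one sentence alone. Section 6.2.2.1.2 also refers to the IPIM, which is not among the documents. It can be said only that the protocol has no recurrence rule for ezetimibe, not that sites lack one.

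Three stronger readings are tempting and are not supported:

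- *That a relapsing control subject gets no permanent stop of ezetimibe, or that sites are told to continue it.* No sentence says so, and the provisions above can stop it. The gap is only that 6.3.3 does not require the stop.
- *That the closing sentence of 6.3.2 keeps ezetimibe going during a hold.* Its lead-in already covers other protocol-required therapies, so this is an inconsistency to tidy.
- *That the 20 of 60 subjects planned for control measure the impact.* That is the allocation, not a count of subjects affected. The documents give no rate of hepatic holds, rechallenge or recurrence, so no expected number can be given.

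What survives the reply is that the fallbacks are recommended, discretionary or conditional. None is the specific permanent instruction that the rechallenge section sets out to give.

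**Conclusion.** The point holds as a minor fault in a safety rule as written. The recurrence sentence in 6.3.3 is narrower than its own heading and than 6.3.1. During the blinded 12 weeks it therefore does not itself require a permanent stop of oral IP on recurrence.

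The size is very small. The affected window runs from Day 1 to Week 12, in subjects allocated to ezetimibe. A hold prompted by the scheduled Week 8 sample leaves 0 to 6 oral dosing days if rechallenge waits four weeks, and about 14 if it came after two. Rechallenge is further limited by the need for an alternative cause, resolved laboratory values and unanimous agreement.

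The conclusion rests on reading ezetimibe as an other protocol-required therapy and on the protocol text alone, without the IPIM. SAP 10.1 refers to a completed primary analysis, which was planned for after all subjects had passed Week 24 or left the study. This is therefore a judgment on the plan as written, not on how any subject was managed.

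**What to change.** In the recurrence sentence of 6.3.3, replace evolocumab with: *all IP: SC IP (evolocumab or placebo) and, through Week 12, PO IP (ezetimibe or placebo)*. Use the same words in the closing sentence of 6.3.2 so that it matches its lead-in. The terms are those the protocol already uses in 9.2.1, and the rule then works without unblinding.

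The cost is two sentence edits. Visits, data collection, blinding, sample size and analysis do not change. With the oral period over in this trial, the practical value lies in correcting the text and in not carrying it into another double-dummy protocol.

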6.4 Concomitant Therapy, Diet, and Exercise

Throughout the study, investigators may prescribe any concomitant medications or treatments deemed necessary to provide adequate supportive care except for those listed in [Section 6.7](#).

Subjects should maintain their current regimen of diet and exercise. Subjects will be required to refrain from unaccustomed intensive exercise (eg, heavy lifting or long runs) 48 hours prior to each visit.

6.5 Medical Devices

Amgen SC IP (evolocumab/placebo) will be administered per prefilled AI/Pen or 3.5 mL Personal Injector, provided by Amgen. Additional details regarding the use of the AI/Pen or Personal Injector is provided in the IPIM and in the Instructions for Use (IFU) brochure. **Other medical devices** (eg, syringes, sterile needles, alcohol prep pads), **which are not considered test articles, may be used in the conduct of this study as part of standard care. These devices** are commercially available are not usually provided or reimbursed by Amgen (except, for example, if required by local regulation). The investigator will be responsible for obtaining supplies of these devices.

6.6 Product Complaints, Including Device Complaints

A product complaint is any written, electronic or oral communication that alleges deficiencies related to the identity, quality, durability, reliability, safety, effectiveness, or performance of a drug or device after it is released for distribution to market or clinic by either Amgen or by distributors and partners for whom Amgen manufactures the material. **This includes any drug(s), device(s), or combination product(s) provisioned and/or repackaged/modified by Amgen. Drugs or devices include evolocumab/placebo, prefilled AI/Pen, and Personal Injector.**

Concerns or irregularities about the packaging, appearance or usage of the prefilled AI/Pen or Personal Injector must be reported to Amgen within 24 hours of discovery or notification of the concern or irregularity. Should any such concerns or irregularities occur please do not use the prefilled AI/Pen or Personal Injector until Amgen confirms that it is permissible to use.

Examples of potential product complaints that need to be reported to Amgen include, but are not limited to:

- broken container or cracked container,
- subject or healthcare provider cannot appropriately use the product despite training (eg, due to malfunction of the prefilled AI/Pen or Personal Injector),

- missing labels, illegible labels, incorrect labels, and/or suspect labels,
- change in IP appearance, for example color change or visible presence of foreign material,
- unexpected quantity or volume, for example amount of fluid in the prefilled AI/Pen or Personal Injector, or
- evidence of tampering or stolen material.

If possible, please have the prefilled AI/Pen or Personal Injector available for examination when making a product complaint. Maintain the prefilled AI/Pen or Personal Injector at appropriate storage conditions until further instructions are received from Amgen.

The investigator is responsible for ensuring that all product complaints, including device complaints, observed by the investigator or reported by the subject that occur after signing of the **informed consent form (ICF)** through 30 days after the last dose of IP or EOS, whichever is later, are reported to Amgen within 24 hours of discovery or notification of the product **and/or device** complaint.

Any product complaint(s) associated with an investigational product(s) or non-investigational product(s) or device(s) supplied by Amgen are to be reported according to the instructions provided in the IPIM.

